Our overriding hypothesis is that radiation interacts, enhances, and potentially accelerates the individual patient's genetic predisposition to develop breast cancer, but does not fundamentally alter the molecular phenotype. To test this hypothesis, we plan to obtain the 54 (or more if available) formalin-fixed, paraffin-embedded tissue samples of the secondary breast cancer cases from the CCSS bio-repository from women who received thoracic radiation. We plan to subject these samples to RNA extraction, using established protocols that yield expression profiles that are highly concordant with frozen tissue.¹²⁻¹³ This mRNA will then be assayed for quality and quantity and amplified accordingly.¹⁴ The resultant cDNA will then be hybridized, at our core facility, using the Affymetrix U133A gene chip. Using the GeneSpring software platform, gene expression data will then be analyzed using supervised methods (which will query the expression levels of specific, hallmark genes that define the molecular subtypes of breast cancer) as well as unsupervised methods (within the set of 54 cases as well as in conjunction with 1,619 general population cases) to determine the prevalence of known, and potentially novel, molecular subclasses of these secondary tumors. Once the subclass designation is established for the 54 secondary breast cancers, the patient demographics and overall survival time after diagnoses will be compared to their spontaneous/general population

counterparts. Generating this working data will enable us to answer the following clinically important questions, which represent our specific aims:

- Specific Aim 1: What is the prevalence/distribution of Luminal A, Luminal B, Basal, Her2-enriched and breast-like breast cancer subtypes among those women who received thoracic radiation during childhood for their pediatric malignancy versus that observed in the general population of spontaneous breast cancers? Consistent with our overriding hypothesis is that the prevalence of these molecular subtypes will approximate that observed in the general, spontaneous breast cancer population. Therefore, assuming radiation induced breast cancers are representative of the general population, approximately 50% will be Luminal A, 20% will be Luminal B, 20% will be Basal, and 10% will be Her 2+.

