 - e. Primary and secondary breast cancer with any hormone status, including ER+, PR+/-, Her2neu-; ER+,PR+/-, Her2neu +; ER-,PR-, Her2neu-; ER-/PR-, Her2neu +

Exclusion criteria

- 1. Previously published research using gene expression data sets for primary breast cancers previously treated with chemotherapy, hormone therapy, or radiation prior to analysis will not be used for the control population
- 2. Previously published research using gene expression data from cell lines and animal studies will not be used for the control population
- 3. Non-epithelial breast malignancies, including lymphoma or sarcoma of the breast and melanoma and non-melanomatous skin cancers
- 4. In situ carcinomas of the breast

Materials/Data needed from the CCSS

- 1. Adequate secondary breast cancer tissue, from the study patients, to yield sufficient, amplifiable mRNA for eventual hybridization with the Affymetrix U133A Gene Chip.
 - a. N=54 (or more if possible)
 - b. At least five 10-micron scrolls (or equivalent quantity) of tumor tissue, verified by corresponding H&E slide, for each sample
- 2. Clinical data on study patients:
 - a. Age at childhood cancer diagnosis
 - b. Childhood primary tumor diagnosis
 - c. Childhood radiotherapy details (including total body irradiation and pelvic radiotherapy)
 - i. Dose and fractionation to irradiated site

- ii. Radiation dose to the chest
- iii. Age at start of radiation
- d. Age at breast cancer diagnosis
- e. Menopausal status at breast cancer diagnosis
- f. Age at death or last follow-up with current vital status for survival calculations
- g. Use of chemotherapy for treatment of the primary cancer

Statistical and Analytic Plans:

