The first layer of analysis will consist of determining the distribution of the molecular subtypes of the secondary breast cancers. The RNA will be isolated from the study samples and in a manner similar to the clustering analysis of the control population, the gene expression status of the 249 genes that define the molecular subclasses will be performed in an unsupervised manner on the 54 study and 1,619 control cases together. To account for batch-effect and paraffin extraction, log-transformation and normalization using the RMA method will be performed, again using GeneSpring software, with all cases included. Genes will undergo an independent QA process (to determine if there is signal susceptibility to the formalin fixation and parafinization process) and will be excluded from the final clustering analysis. The placement of the study cases within the cluster groups, as defined predominantly by the control population, will determine the subclass assignment. A chi-square test will be used to compare the distribution of molecular subtypes between the primary and secondary breast cancers.

The raw data from the .cel files of the study population will also be compared. This will be especially important in the event of the formation of a separate clustering group by the radiation-induced cases and a novel subtype is identified. From this analysis, the genes that define this new subclass will be identified and reported. This approach will also allow the identification of gene expression, unique to previously radiated breast tissue, which spans across all subtypes.

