To study our second aim, the molecular subtype status of the study population will be analyzed as a clinicopathologic factor for it's association with survival as well as with other factors such as age at childhood cancer diagnosis, type of childhood primary malignancy, age at time of radiation for childhood malignancy, radiation dose to the chest during childhood, total radiation dose received during childhood, use of chemotherapy for treatment of childhood malignancy, age and menopausal status at breast cancer diagnosis, and stage at breast cancer diagnosis. Correlative analysis (Spearman's rho, t-tests, ect.) will be used to test for univariable associations between the molecular subtype and the cross-sectional demographic variables. For the time-to-event outcomes such as survival and time to onset of breast cancer the log-rank test will be used to determine univariate associations of the molecular subtype (key risk factor of interest) with these outcomes intervals. Additional risk factors such as age at childhood cancer diagnosis, age at time of radiation for childhood malignancy, and radiation dose to the chest during childhood will also be evaluated similarly. Cox proportional hazards models will be used to evaluate multivariable associations between molecular subtype and each of the time-to-event outcomes, adjusting for other factors found to be significant in univariable analyses, or considered *a priori* to be important to include in the model (e.g. age at diagnosis, breast cancer stage, etc.)

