The CCSS database represents the only chance in which the issue of the breast cancer molecular subclass prevalence, in the setting of previous thoracic radiation, could possibly be addressed. If any single institution attempts to do this, there would not be enough cases to draw a statically significant conclusion. Fortunately, there are 54 cases within the CCSS database, and this is sufficient to determine if the 5 molecular subtypes are evenly distributed, or predominately composed of 1 or 2 subtypes. In the most diffuse scenario, if there are at least 10 samples per subtype (5), there will be a >80% power to detect a 2-fold difference between any of the two groups using Chi-squared analysis. A coefficient of variation of 50% and alpha = 0.005 (.05/10, to adjust for 10 comparisons between 5 groups) will be used for the calculations. Since we expect there to be 50% with the Luminal A subtype designation, there will be even greater power to make this conclusion statistically valid. It should be iterated, though, that regardless of statistical power, this is a retrospective study and the large number of subjects from the CCSS provide the only means for attempting to answer this scientific question.

Figures:

Hierarchical clustering of 115 tumour tissues and seven non-malignant tissues using the "intrinsic" gene-set. (A) A scaled-down representation of the entire cluster of 540 genes and 122 tissue samples based on similarities in gene expression. (B) Experimental dendrogram showing the clustering of the tumours into five subgroups. Branches corresponding to tumours with low correlation to any subtype are shown in grey. (C) Gene cluster showing the *ERBB2* oncogene and other co-expressed genes. (D) Gene cluster associated with luminal subtype B. (E) Gene cluster associated with the basal subtype. (F) A gene cluster relevant for the normal breast-like group. (G) Cluster of genes including the oestrogen receptor (*ESRI*) highly expressed in luminal subtype A tumours. Scale bar represents fold-change for any given gene relative to the median level of expression across all samples. PNAS, July 8, 2003, vol. 100, no. 14, 8418–8423. Copyright (2003) National Academy of Sciences, USA.

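### Spearman's rho and t-tests are named for associations with molecular subtype, an unordered factor with four or five levels; one global test per variable should replace them

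*Protocol*

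**What the plan says.** All references are to the protocol.

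- **Tests named.** Statistical and Analytic Plans, paragraph on the second aim: Spearman's "rho, t-tests, ect.) will be used to test for univariable associations between the molecular subtype and the cross-sectional demographic variables". The same paragraph lists nine factors to be related to subtype. They include "type of childhood primary malignancy, age at time of radiation for childhood malignancy, radiation dose to the chest during childhood", as well as total radiation dose, chemotherapy use, menopausal status and breast cancer stage.
- **What subtype is.** Statistical and Analytic Plans, first paragraph: "The placement of the study cases within the cluster groups, as defined predominantly by the control population, will determine the subclass assignment". It is therefore membership of a cluster, with no order defined.
- **How many levels.** Specific Aim 1 expects four: "approximately 50% will be Luminal A, 20% will be Luminal B, 20% will be Basal, and 10% will be Her 2". The sample-size paragraph works with five: "this is sufficient to determine if the 5 molecular subtypes are evenly distributed, or predominately composed of 1 or 2 subtypes".
- **Multiplicity.** The only statement is in the sample-size paragraph: "alpha = 0.005 (.05/10, to adjust for 10 comparisons between 5 groups) will be used for the calculations". It belongs to a power calculation described as chi-squared and is not linked to the tests above.
- **Number of cases.** Materials/Data needed from the CCSS: "N=54 (or more if possible").

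**The concern.** Spearman's rho ranks both variables. Luminal A, luminal B, basal, HER2-enriched and normal-like have no natural rank, so a single rho across them reflects whatever numbering the analyst chose. A t-test compares two groups, so covering every pair takes 6 tests per variable with four classes and 10 with five. Type of childhood malignancy is itself nominal, so neither test can relate it to a subtype with several levels.

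At stake are the reported associations of subtype with patient and treatment factors among the secondary breast cancers. A real association could be missed, or its sign reversed, because of label order. A chance association could be reported because many pairs were tried.

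**Working it through.** **The plan's own figure.** Pairs among five groups: 5 × 4 / 2 = 10, and 0.05 / 10 = 0.005. The stated alpha reproduces exactly. It shows that the authors counted the pairwise comparisons when planning power.

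**Inputs.**
- N = 54 (protocol).
- Four-class sizes from Specific Aim 1: 0.50 × 54 = 27; 0.20 × 54 = 10.8, taken as 11, twice; 0.10 × 54 = 5.4, taken as 5. The sum is 27 + 11 + 11 + 5 = 54.
- Five-class sizes: an even split, 11/11/11/11/10 (assumed, for the evenly distributed case).
- Effect sizes: the protocol gives none for these variables, so the shifts below are assumptions.
- Normal data with SD 1, two-sided 0.05.

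**Step 1: label order and Spearman's rho.** Four labels can be ordered in 4! = 24 ways. Reversing an order only flips the sign of rho, which leaves 24 / 2 = 12 distinct codings. For each coding, rho is tested with t = rho × √(52 / (1 − rho²)) on 52 degrees of freedom, in 2,000 simulated data sets of 54.

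| Assumed shifts (SD), groups of 27/11/11/5 | Spearman power, worst to best label order | Kruskal-Wallis power |
|---|---|---|
| A: 0 / 0 / −1 / 0 | 6% to 54% | 61% |
| B: 0 / 0.4 / −0.8 / 0.4 | 2% to 80% | 65% |

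In scenario A the mean rho ranges from −0.276 to +0.274 across the codings. In scenario B a single simulated data set gave p from 0.003 to 0.94, depending only on the order chosen. In B the luckiest order beats Kruskal-Wallis, but nobody could know in advance which order that is.

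**Step 2: all-pairs t-tests with no true difference.** 20,000 simulated data sets, pooled t-tests, each at 0.05.

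| Groups | Tests per variable | Family-wise error, simulated | Independence formula 1 − 0.95^m |
|---|---|---|---|
| 4 (27/11/11/5) | 6 | 21% | 1 − 0.95^6 = 26% |
| 5 (11/11/11/11/10) | 10 | 28% | 1 − 0.95^10 = 40% |

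The simulated figures are lower because the pairs share groups, and they are the ones to use. With Bonferroni adjustment (0.05/6 and 0.05/10) the error falls to about 3.9% and 4.1%.

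**Step 3: fit by type of variable.** Of the nine factors, five are continuous (three ages, two doses), stage is ordinal, malignancy type is nominal, and chemotherapy use and menopausal status are binary. For the continuous variables and stage, rho fails because subtype is unordered, and a t-test covers only one pair at a time. For malignancy type neither variable has an order or a mean, so neither named test applies. For the two binary factors against a subtype with several levels, a contingency-table test is needed. The only one in the plan is the chi-square, and it is assigned to comparing subtype distribution between primary and secondary cancers.

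**The case against.** The strongest defence is that nothing in the protocol says subtype will be numbered 1 to 4 or 1 to 5. If each subtype is coded as an indicator (that subtype versus the rest), rho and the t-test are both valid, and rho between two binary indicators is the phi coefficient. In scenario A, Spearman on the indicator of the shifted subtype has about 81% power. Testing all four indicators at 0.05/4 gives about 65%, close to Kruskal-Wallis. This is correct, and it makes the 6% to 54% range conditional on numeric coding. It does not rescue the sentence, because the protocol specifies neither indicator coding nor a collapse to two groups.

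The list of tests is also open-ended, so a suitable test is not excluded. That is true, but the two tests actually chosen are the ones that do not fit. The point is a stated method, not a missing detail.

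On multiplicity, the paragraph is silent; it does not rule adjustment out. If the 0.005 of the sample-size paragraph were applied to all pairs, the family-wise error would be about 2.5% (four groups) or 4.2% (five). The protocol makes no such link, but it does not state an all-pairs strategy at 0.05 either, so the 21% and 28% are conditional too.

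A reader might infer two stronger conclusions, and the document supports neither:
- *That these results select covariates for the Cox models and so distort the survival analysis.* The sentence relates subtype to other factors, not any factor to survival. The log-rank screen follows it, and the Cox adjustment for factors significant in univariable analyses most naturally means that screen. Age at diagnosis and stage are also given as covariates chosen in advance.
- *That the whole demographics endpoint is compromised.* The methods overview also compares demographics between cases and the general-population controls. That is a two-group comparison, for which a t-test on age is suitable.

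**Conclusion.** The concern holds, with limited reach. As written, the two named tests do not fit an unordered factor with four or five levels, and the plan gives no coding or global test that would make them fit. That mismatch, and the dependence of rho on label order under numeric coding, need no assumption about effect size.

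The sizes are illustrative. The power range of about 6% to 54% against 61% rests on numeric coding, sizes 27/11/11/5 and a 1 SD shift in one subtype. The family-wise error of about 21% or 28% per variable rests on all pairs being tested at 0.05, with normal data and the group sizes shown.

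The primary chi-square comparison and the log-rank analyses are untouched, as are the Cox models on the natural reading. The sentence should be corrected, but the main conclusions of the study do not hang on it.

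**What to change.** Replace the sentence on correlative analysis with one global test per variable, within the cases:

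- Kruskal-Wallis (or ANOVA) for ages and doses, and Kruskal-Wallis for ordinal stage.
- Fisher-Freeman-Halton exact test for type of childhood malignancy, chemotherapy use and menopausal status.
- Pairwise contrasts between subtypes only after a significant global test, with Holm adjustment within each variable.
- T-tests kept for true two-group comparisons, such as age in cases versus controls.

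While editing, state that the univariable screen for the Cox models means the analyses against the time-to-event outcomes, so that the other reading is closed.

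The cost is a change of wording. It needs no new data and no more cases, and it is best made before the subtype assignments are known.

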- 2. Specific Aim 2: Is there a clinical outcome difference in terms of overall survival after diagnosis within the molecular subclasses of the 54 cases of secondary breast cancers from the childhood cancer survivors and compared to spontaneous breast cancers from the general population cases with the same molecular subclass? We believe the answer to this question will determine if radiation has an independent role in expediting the development of various breast cancers and/or augmenting the biologic lethality of the disease.

If our overriding hypothesis is incorrect, then 2 other potential phenomena may be identified with this data:

- 1. Radiation to the chest during childhood induces a specific type of one of the established molecular subclasses of breast cancer, which may or may not have the same virulence as seen in the general breast cancer population.
- 2. A novel molecular subclass(es), unique to patients with radiation to the chest during childhood, is elucidated. If so, multiple questions can be answered using this data:
 - i. What are the hallmark genes that define this group?
 - ii. What are the patient demographics at time of onset? And
 - iii. What is the expected survival time within this group(s)?

Analysis framework:

Outcome of interest

Primary endpoint:

- The patterns of gene expression and distribution of molecular subtypes of radiation induced breast cancer compared to spontaneous/primary breast cancer

Secondary endpoints:

- Overall survival: Time from diagnosis of breast cancer to death of any cause
- Patient demographics at the time of breast cancer diagnosis.

Subject population:

Inclusion criteria

- 1. Cases: Survivors from the Childhood Cancer Survivor Study Cohort who subsequently developed breast cancer after thoracic radiation, with available breast tissue
- 2. Controls: 1,619 patients with spontaneous primary breast cancers, without previous cancer diagnosis or treatment, obtained from previously published research studies for which the gene expression data is publically available, will comprise the general, spontaneous breast cancer population. The previously published gene expression data is analyzed for subtype composition and is presented in **Figure 2**.¹⁵⁻²²
 - a. All ages
 - b. All stages
 - c. Tumor sample obtained from biopsy or surgical specimen prior to any non-surgical therapy
 - d. Biopsy proven invasive ductal, lobular, mucinous, tubular, colloid or papillary (i.e. epithelial) carcinoma of the breast

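### Time to onset is tested by log-rank and Cox in women who all have breast cancer, so the results describe timing among the diagnosed, not the rate of onset

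*Protocol*

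**What the plan says.** - **Cases** (Protocol, Subject population, Inclusion criteria 1): "Survivors from the Childhood Cancer Survivor Study Cohort who subsequently developed breast cancer after thoracic radiation, with available breast tissue".
- **Controls** (Inclusion criteria 2): "1,619 patients with spontaneous primary breast cancers, without previous cancer diagnosis or treatment". They too all have breast cancer.
- **Data request** (Materials/Data needed from the CCSS): "N=54 (or more if possible"; the clinical items are requested for the study patients. They include "Age at breast cancer diagnosis" and "Age at death or last follow-up with current vital status for survival calculations". The second item is tied to survival, not to censoring for onset.
- **Analysis** (Statistical and Analytic Plans, paragraph on the second aim): "For the time-to-event outcomes such as survival and time to onset of breast cancer the log-rank test will be used to determine univariate associations". Subtype is called the key risk factor. Age at childhood diagnosis, age at radiation and chest dose are to be handled in the same way. Then: "Cox proportional hazards models will be used to evaluate multivariable associations between molecular subtype and each of the time-to-event outcomes".
- **Intended conclusion** (Specific Aim 2): "We believe the answer to this question will determine if radiation has an independent role in expediting the development of various breast cancers". The sentence goes on to add the lethality of the disease as a second possible conclusion.

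**The concern.** A log-rank test or Cox model for onset compares, at each time, the woman who develops cancer with women still at risk. Here the women still at risk are only those who will be diagnosed later. Irradiated survivors who never developed breast cancer carry the information on whether chest dose or age at radiation changes risk, and they are absent. Observed onset times are also limited to those that fall before the end of follow-up.

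The plan would still produce hazard ratios and p-values under a risk-factor label. A null result for chest dose could be taken as evidence that dose does not affect onset, when the analysis could hardly have shown an effect. If follow-up differs by dose or treatment era, the same analysis could show a strong association where none exists.

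**Working it through.** The protocol gives no effect size, event count or power for onset, so there is no figure to reproduce. Its one power statement concerns the subtype comparison. The only inputs from the documents are the 54 cases and the selection rule. Incidence, follow-up, hazard shape and effect size below are assumptions, shown over a range.

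**1. Risk set.** Cases: 54, all with the event, none censored for onset. Controls: 1,619, all with breast cancer and without earlier cancer or treatment, so they have no interval from childhood exposure and add no event-free women. The plan names no weights or correction for selection on the event.

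**2. What the case-only analysis sees.** Let H0(t) be the cumulative onset hazard without the factor, h0(t) its derivative, r the true hazard ratio and τ the end of follow-up. Among women diagnosed by τ, the density of onset time is

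r h0(t) exp(−r H0(t)) / [1 − exp(−r H0(τ))].

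When H0(τ) is small this is close to h0(t)/H0(τ), and r cancels.

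As a check, take the time at which H0 has reached half its final value and ask what share of cases is already diagnosed. Let c be the incidence without the factor.
- Without the factor: [1 − √(1 − c)]/c. With r = 2: c/[1 − (1 − c)²].
- c = 10%: (1 − 0.9487)/0.10 = 51.3%, against 0.10/0.19 = 52.6%.
- c = 30%: (1 − 0.8367)/0.30 = 54.4%, against 0.30/0.51 = 58.8%.

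At c = 10% the incidences themselves are 10% and 19%, yet the timing curves among cases nearly coincide.

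**3. Simulation.** Weibull onset (shape 1 and 3), factor in half the cohort, 35 years of follow-up, only women with onset kept, 54 cases, two-sided 0.05, 2,000 replicates per setting. Ranges cover both shapes.

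| Incidence without factor | Case-only HR, true HR 2 | Rejected | Case-only HR, true HR 3 | Rejected |
|---|---|---|---|---|
| 2% | 1.00-1.01 | 5.1-5.8% | 1.00-1.01 | 5.3-6.1% |
| 5% | 1.00-1.02 | 5.4-6.0% | 1.03 | 5.9-6.4% |
| 10% | 1.03 | 5.3-5.5% | 1.04-1.05 | 5.7-6.5% |
| 20% | 1.05-1.06 | 5.2-5.4% | 1.12 | 6.8-6.9% |
| 30% | 1.09-1.10 | 6.2-6.8% | 1.19-1.20 | 9.4-9.7% |

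Staggered follow-up of 15-40 years (shape 3, incidence 5-30%) gives case-only HRs of 1.02-1.11 with 5.5-6.7% rejected for true HR 2, and 1.05-1.23 with 6.6-10.6% rejected for true HR 3. The effect reappears only at very high incidence. For true HR 2 the case-only HR is 1.19 (11% rejected) at 50% incidence and 1.35 (20%) at 70%.

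**4. Comparator.** With 54 events in a full irradiated cohort and a 50:50 factor, Schoenfeld's formula gives power Φ(√(54 × 0.25) × ln HR − 1.96).
- HR 2: Φ(3.674 × 0.693 − 1.96) = Φ(0.587) = 72%.
- HR 3: Φ(3.674 × 1.099 − 1.96) = Φ(2.08) = 98%.

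A separate simulation of the HR 2 case gave 68-72% for the cohort and 6-7% for the case-only test.

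**5. Follow-up that differs by factor level.** Take 25-40 years in the exposed, 15-30 years in the unexposed, and incidence 5-20%. With a true HR of 1 the case-only HR is 0.28-0.29 and about 98% of tests reject. With a true HR of 2 it is 0.29-0.32, which is the wrong direction.

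**6. Specific Aim 2.** The question posed there is survival after diagnosis, within subtypes and against spontaneous cancers of the same subtype. Survival after diagnosis says nothing about how soon cancer arose. The onset analysis has no unirradiated group, since every case was irradiated. Neither supports a conclusion that radiation expedites development.

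**The case against.** **Onset is not a listed endpoint.** Correct. Outcome of interest lists subtype patterns as primary, and overall survival and demographics as secondary. The chi-square comparison of subtypes and survival after diagnosis do not depend on the onset analysis. This limits the severity but does not remove the error, because the plan assigns onset formal tests and risk-factor language.

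**Subtype latency among cases is a fair question.** This also stands. Without censoring, the log-rank test is a valid rank test of equal latency between subtypes. A reader might infer that even this comparison is invalid, or that its failure to flag a subtype with three times the incidence of another is a fault. Neither follows: if latency does not differ, about 5% rejection is correct, and subtype frequency is tested elsewhere by chi-square. The comparison is blunt, though. With 10% incidence and 35 years of follow-up, a true delay of 3 or 5 years in one group was detected in only 6-7% of simulated studies.

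**False positives for age at radiation.** A reader might point out that, when onset depends on attained age only, the case-only test rejects for age at radiation in roughly 7-12% of studies. That is not evidence of a case-only artefact. It comes from the time scale, and a full cohort analysed on latency rejects more often (16-75%, depending on the assumed radiation ages).

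**A different test would not help.** Kruskal-Wallis on the same case-only times behaves like the log-rank test (5-6% for a true HR of 2). The label and the inference have to change, not the test statistic.

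**The stated purpose concerns survival.** A reader might infer that the protocol plans to use the onset results to show that radiation expedites cancer. The text ties that claim to the survival question. The claim is unsupported either way.

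**Conclusion.** The plan is wrong as written, with moderate severity. Its selection rule, data request and onset models are incompatible. Case-only hazard ratios for chest dose, age at radiation and age at childhood diagnosis measure timing among the diagnosed, not the rate of onset. Detection of a true doubling is about 5-7% with 54 cases, barely above the 5% error rate, against about 70% in a cohort with 54 events. This rests on assumed proportional hazards, follow-up unrelated to the factor, and cumulative incidence up to about 30%; the protocol states none of these. If follow-up is related to the factor, the estimate is biased and can point the wrong way.

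A stronger reading, that the study's main results are compromised, is not supported: the primary comparison, survival after diagnosis and a properly labelled description of latency by subtype all remain usable.

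**What to change.** 1. In Statistical and Analytic Plans (second aim), remove age at childhood diagnosis, age at radiation and chest dose as log-rank or Cox risk factors for onset, and remove the Cox model for onset. Leave the survival analyses as they are.
2. Report latency by subtype as *latency among diagnosed cases*, with a sentence that no inference on risk or rate of onset is drawn.
3. In Specific Aim 2, delete the claim that the answer will show whether radiation expedites development of breast cancer. Keep the part on lethality, which the survival contrast addresses.
4. Estimate risk-factor effects on onset only if follow-up on irradiated survivors without breast cancer can be obtained (full cohort, case-cohort or nested case-control). The documents do not show that it can. Subtype-specific models would be thin even then: the protocol's expected 50/20/20/10% split of 54 cases gives about 27, 11, 11 and 5 events.

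Items 1 to 3 change wording only. The study gives up a claim about onset that its data cannot support. Item 4 would need a new data request.

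### The log-rank test of subtype in 54 women, read against chi-square, rejects too often (about 6–9% at nominal 5% on the plan's own subtype sizes); a permutation p-value restores the level

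*Protocol*

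**What the plan says.** The test is set out in the Protocol, Statistical and Analytic Plans, in the paragraph on the second aim. It is run within the irradiated cases: "the molecular subtype status of the study population will be analyzed as a clinicopathologic factor". The outcomes are named next: "For the time-to-event outcomes such as survival and time to onset of breast cancer the log-rank test will be used". Subtype is the main factor: "the log-rank test will be used to determine univariate associations of the molecular subtype (key risk factor of interest". Other risk factors are to be evaluated in the same way, and univariable significance is one route by which a factor enters the Cox models. No reference distribution, exact version or permutation version is mentioned.

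Three other places fix the group sizes.
- The sample-size paragraph gives the number of cases: "Fortunately, there are 54 cases within the CCSS database".
- Specific Aim 1 lists five subtypes, "Luminal A, Luminal B, Basal, Her2-enriched and breast-like breast cancer subtypes", but gives expected shares for four: "approximately 50% will be Luminal A, 20% will be Luminal B, 20% will be Basal, and 10% will be Her 2".
- The sample-size paragraph also considers an even spread: "if there are at least 10 samples per subtype (5), there will be a >80% power to detect a 2-fold difference". This concerns a chi-squared comparison, not the log-rank test.

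Under the inclusion criteria every case already has breast cancer. Time to onset therefore has 54 events and no censoring.

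**The concern.** The chi-square reference for a K-group log-rank statistic is a large-sample approximation. It needs a reasonable expected number of events in each group. With 54 women in four or five groups, the statistic has a heavier right tail than chi-square, so a p-value of 0.05 is reached too often when subtypes do not differ.

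Aim 2 asks whether overall survival differs between subtypes among these cases, and the log-rank test is the stated univariable test of that question. An excess of false positives could present one or two early deaths in a small subtype as a subtype effect. The protocol regards this cohort as the only means of addressing its question, so such a result would be hard to check elsewhere. The same leniency can affect which grouped factors are carried into the Cox models.

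**Working it through.** **Inputs from the protocol.** There are N = 54 cases. The expected shares 50/20/20/10% give 0.50 × 54 = 27, 0.20 × 54 = 10.8 (twice) and 0.10 × 54 = 5.4, or about 27/11/11/5. These total 54, so nothing is left for the breast-like subtype. The even five-way split is 54/5 = 10.8, or 11/11/11/11/10. Events are 100% for time to onset.

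**Assumptions.** The protocol gives no number of deaths and no share for the breast-like subtype. I take 30–100% events and, where that subtype is tested separately, 2 to 5 women in it. At 30% events there are 0.30 × 54 ≈ 16 deaths. A group of 5 then expects about 1.5 deaths and a group of 2 about 0.6.

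**Statistic.** At event time j, d_j of the n_j women at risk have the event, and n_kj of those at risk are in group k.
- E_k = Σ d_j n_kj / n_j
- V_kl = Σ d_j [(n_j − d_j)/(n_j − 1)] (n_kj/n_j)(δ_kl − n_lj/n_j)
- X² = (O − E)′ V⁻ (O − E), compared with chi-square on K−1 df

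**Why the tail is heavy.** Take a group of 2 whose members both die before anyone else.
- O = 2 and E = 2/54 + 1/53 = 0.0559.
- V = (2/54)(52/54) + (1/53)(52/53) = 0.0357 + 0.0185 = 0.0542.
- (2 − 0.0559)²/0.0542 ≈ 70, and the K-group X² is at least this large.
- Yet under no difference this ordering has probability 1/(54 × 53/2) = 1/1431, far more than chi-square on 4 df allows for a value of 70.

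**Null simulation.** Times were exponential and the nominal level was 5%. There were 40,000 replicates per setting, and fewer for the 11/11/11/11/10 row. The statistic matched a standard package. The table gives rejection rates in %; the censored columns show the event fraction and type of censoring.

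| Sizes | all 54 events | 50%, random | 30%, random | 50%, admin. | 30%, admin. |
|---|---|---|---|---|---|
| 27/11/11/5 | 8.8 | 7.6 | 7.0 | 6.7 | 5.9 |
| 11/11/11/11/10 | 8.7 | 7.2 | 6.5 | 6.5 | 5.5 |
| 26/11/10/5/2 | 13.1 | 11.6 | 10.7 | 10.7 | 9.1 |
| 26/10/10/5/3 | 11.4 | 10.2 | 9.6 | 9.2 | 7.4 |
| 25/10/10/5/4 | 10.6 | 9.2 | 9.1 | 8.0 | 7.1 |
| 24/10/10/5/5 | 10.2 | 9.0 | 8.4 | 7.7 | 6.8 |

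With sizes drawn at random from the four stated shares, the range is 6.4–9.2%. As calibration, five groups of 200 give 5.2%, so the excess comes from the small sample and not from the code.

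**Permutation reference.** With 399 relabellings and 2,500 replicates per setting, rejection was 4.2–5.3% for 26/11/10/5/2 and 4.6–5.9% for 24/10/10/5/5 (simulation error about ±0.9 points). The chi-square reading of the same data gave 10.4–13.0% and 7.8–10.1%. When censoring was made clearly unequal across subtypes, permutation gave 3.4–5.9%.

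**The case against.** The strongest reply is that the protocol does not say chi-square. It names the log-rank test, which is conventional, and a statistical analysis plan could specify a permutation version. This stands in part: the chi-square reference is the default meaning of the named test, not written text, and the protocol contains no false statement here. But the protocol does fix the test, and its own sizes make the default reading unsuitable. The point is therefore a better method, not a missing detail.

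Second, a reader might infer that the test errs about twice as often as stated, at roughly 9–12%. The documents do not support this as the headline. It needs a fifth group of about 2 women, and the stated shares already reach 100% over four subtypes. The background section also says the normal-like group may reflect poorly sampled tumor, and the protocol does not say whether it would be a separate stratum for survival.

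Third, the excess depends on the number of deaths. At 20% events with administrative censoring, the four-group rate is 5.7% and the even five-way rate is 5.0%.

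Fourth, overall survival is a secondary endpoint, time to onset is not a listed endpoint, and no alpha is attached to the log-rank test. The 0.005 in the sample-size paragraph belongs to the chi-squared calculation and should not be carried over. All of this limits the weight of the point but does not remove it.

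**Conclusion.** The concern holds in a moderate form. On the plan's own sizes, the default chi-square reading gives a false-positive rate of about 6–9% at nominal 5%, over 30–100% events. For survival at 30–50% events it is about 5.5–7.6%, and for time to onset 8.7–8.8%.

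If a breast-like subtype of 2 to 5 women is tested separately, the range is about 7–13%: 6.8–11.6% for survival at 30–50% events and 10.2–13.1% for time to onset. The size of that group and the number of deaths are assumptions.

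Tiny groups make the problem worse but are not its only source, since the even split also exceeds 5% in the settings tabulated. A rule that applied the remedy only to factors with very small levels would therefore miss part of it. The point concerns a secondary analysis and says nothing about the chi-square comparison in Aim 1.

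**What to change.** In the second-aim paragraph of Statistical and Analytic Plans, keep the log-rank statistic and add that its p-value is taken from random permutation of the subtype labels (for example 10,000 permutations), for both survival and time to onset. Apply the same to the other grouped factors tested by log-rank in the 54 cases.

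The cost is one sentence and seconds of computing; the data, statistic and hypothesis do not change. The small downside is that the permutation p-value is exact only if censoring is similar across subtypes. In simulation it stayed at about 3–6% under clearly unequal censoring, and time to onset has no censoring. The Cox models are left as they are, so their own sparse subtype groups are not addressed by this change.
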